2.2 Secondary objective(s)

- To evaluate the efficacy of sirolimus in combination with durvalumab as neoadjuvant treatment for Stage I, II, and IIIA NSCLC by Investigator-assessed response rate per RECIST v1.1, disease free survival and overall survival
- To evaluate response to sirolimus in combination with durvalumab in patients with PD-L1-positive vs. PD-L1-negative tumors by complete pathologic response rate
- To evaluate the association between blood mutation burden and response to sirolimus and durvalumab by overall response rate in PD-L1-positive and PD-L1-negative groups based on mutational burden.
- To evaluate impact of neoadjuvant durvalumab and sirolimus on post-surgical recovery by length of hospital stay after surgery

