4.3 Withdrawal of patients from study treatment and/or study

Stopping Rules:

Patients must discontinue study treatment if they experience any of the following:

- Pregnancy
- Radiographic and/or symptomatic deterioration attributed to disease progression disease as determined by the investigator
- Intolerable toxicity related to sirolimus and/or durvalumab, including development of an irAE determined by the investigator to be unacceptable given the individual patient's potential response to therapy and severity of the event
- Any medical condition that the investigator or Sponsor determines may jeopardize the patient's safety if he or she continues on study treatment
- Use of another non-protocol-specified anti-cancer therapy

The primary reason for study treatment discontinuation should be documented on the appropriate CRF.

Additional reasons for patient discontinuation include:

- Any medical condition that the investigator or Sponsor determines may jeopardize the patient's safety if he or she continues in the study
- Investigator or Sponsor determines it is in the best interest of the patient
- Patient non-compliance

The Sponsor has the right to terminate this study at any time. Reasons for terminating the study may include, but are not limited to, the following:

Clinical Study Protocol

Investigational Drug Substance: MEDI4736 Sirolimus (Rapamune)

Study Number **19-20015**

Edition Number: 4

Date: **11 February 2022**

- The incidence or severity of adverse events in this or other studies indicates a potential health hazard to patients.
- Patient enrollment is unsatisfactory.

Permanent discontinuation of study treatment

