9.1.2 Radiographic Response Assessment of Anti-tumor effect

For the purposes of this study, patients should be re-evaluated for response prior to surgical resection.

Response and progression will be evaluated in this study using the new international criteria proposed by the revised Response Evaluation Criteria in Solid Tumors (RECIST) guideline (version 1.1)⁴⁶. Changes in the largest diameter (unidimensional measurement) of the tumor lesions and the shortest diameter in the case of malignant lymph nodes are used in the RECIST criteria.

Definitions

Evaluable for toxicity. All patients will be evaluable for toxicity from the time of their first treatment with sirolimus.

Evaluable for objective response. Only those patients who have measurable disease present at baseline, have received at least one cycle of Durvalumab, and have had their disease re-evaluated will be considered evaluable for response. These patients will have their response classified according to the definitions stated below. (Note: Patients who exhibit objective disease progression prior to the end of cycle 1 will also be considered evaluable.)

Evaluable Non-Target Disease Response. Patients who have lesions present at baseline that are evaluable but do not meet the definitions of measurable disease, have received at least one cycle of therapy, and have had their disease re-evaluated will be considered evaluable for non-target disease. The response assessment is based on the presence, absence, or unequivocal progression of the lesions.

Disease Parameters

Measurable disease. Measurable lesions are defined as those that can be accurately measured in at least one dimension (longest diameter to be recorded) as ≥ 10 mm with CT scan, MRI, or calipers by clinical exam. All tumor measurements must be recorded in millimeters (or decimal fractions of centimeters).

Malignant lymph nodes. To be considered pathologically enlarged and measurable, a lymph node must be ≥ 15 mm in short axis when assessed by CT scan (CT scan slice thickness recommended to be no greater than 5 mm). At baseline and in follow-up, only the short axis will be measured and followed.

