11.1.2 Efficacy analysis set

The primary and secondary efficacy analyses will include all enrolled patients who have received at least one dose of durvalumab, underwent resection and who do not have EGFR mutant tumors (efficacy population).

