11.2.2 Efficacy analyses

Primary Efficacy Endpoint

The effectiveness of sirolimus followed by durvalumab will be assessed by complete pathologic response rate in the efficacy population. If the null hypothesis is rejected then this is evidence that the response rate exceeds 10% when sirolimus followed by durvalumab is given before resection. The one-sided 95% confidence interval (CI) for complete pathologic response will be reported. Exact binomial test will be used to compare the estimated complete pathologic response rate to the historical reference.

Secondary Efficacy Endpoints

The complete pathologic response rates for PDL-1 negative and PDL-1 positive patients in the *efficacy population* will be presented separately.

A comparison of both the *complete pathologic response* and investigator assessed response rates per RECIST v1.1 rates between the PD-L1 positive and PD-L1 negative groups will be performed by calculating the lower bound of a one-sided 80% CI for the difference, complete pathologic response for PDL-1 positive patients – complete pathologic response for PDL-1 negative patients. Chi-square test or Fisher's exact test will be used to compare the efficacy in term of response rate between the different groups stratified by other factors, respectively. Logistics regression model will be further employed to test the adjusted effect of each other factor on the response rate after adjusting for other clinical factors and demographic factors, respectively. Correlation of response will be performed for tumor mutation burden using spearman correlation coefficient and tested with Wald's test.

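### Sections 9.1.2 and 11.1.2 give the RECIST response rate two different denominators, and the second depends on a resection that comes after the scan

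*Combined protocol and SAP*

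**What the plan says.** Investigator-assessed RECIST response is a secondary efficacy endpoint. Section 2.2 evaluates efficacy "by Investigator-assessed response rate per RECIST v1.1, disease free survival and overall survival", and Section 11.2.2, under its secondary endpoints, plans a comparison of "investigator assessed response rates per RECIST v1.1 rates between the PD-L1 positive and PD-L1 negative groups".

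Two places say who is counted.

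- Section 9.1.2 counts, in the radiographic assessment, "Only those patients who have measurable disease present at baseline, have received at least one cycle of Durvalumab, and have had their disease re-evaluated". It adds that "Patients who exhibit objective disease progression prior to the end of cycle 1 will also be considered evaluable". Surgery and EGFR status are not mentioned.
- Section 11.1.2, and the efficacy paragraph of the synopsis in the same words, states: "The primary and secondary efficacy analyses will include all enrolled patients who have received at least one dose of durvalumab, underwent resection". The sentence goes on to exclude EGFR-mutant tumors.

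On timing, Section 9.1.2 says that "patients should be re-evaluated for response prior to surgical resection", so the response is read before the event that Section 11.1.2 requires. Section 11.2.2 names no separate set for RECIST, and no text ranks one definition above the other.

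**The concern.** Resection is a natural condition for pathologic response, which can only be read on resected tissue. It is not a natural condition for a scan taken before the operation. Whether a patient reaches surgery is decided after the scan and may depend on what the scan shows. Conditioning the RECIST rate on resection therefore lets a later event, possibly related to the outcome, decide who is counted.

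The practical stake is that two analysts who each follow the document can report different response rates from the same scans. This reaches the overall RECIST rate, the PD-L1 comparison and the Section 2.2 objective relating response to mutation burden. The study is open-label and single-arm with investigator-read response, so leaving the set to be chosen once results are known is undesirable.

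**Working it through.** **The plan's own figure.** The only design calculation concerns pCR (Section 11.3): 16 + 15 = 31 patients, continue with at least 2 of 16, success with at least 6 of 31, 10% against 25%, one-sided alpha 0.1, power 80%. The probability of success at rate p is the sum over x1 ≥ 2 of P(X1 = x1 | 16, p) × P(X2 ≥ 6 − x1 | 15, p). It equals 0.0788 at p = 10% and 0.8053 at p = 25%, and a search for the minimax design returns the same N and cut-offs. The stated design reproduces and does not use RECIST response.

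**The two rules applied to the same records.** Assume that each patient has measurable disease at baseline and one cycle of durvalumab. Tumors are not EGFR-mutant unless stated.

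| Record | Section 9.1.2 | Section 11.1.2 |
|---|---|---|
| Progression on the pre-surgery scan, resected | non-responder | non-responder |
| Progression on the pre-surgery scan, not resected | non-responder | not counted |
| Response on the scan, not resected (for example, toxicity) | responder | not counted |
| Response on the scan, resected, EGFR-mutant | responder | not counted |
| Never re-scanned, not resected | not counted | not counted |

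The middle three rows are the conflict. The last row is a gap shared by both rules, not a contradiction.

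**Size of the resection effect.** Let E be the number evaluable under 9.1.2, R the responders among them, k the number of these not resected, and j the responders among the k. Leave EGFR status aside.

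- Rate under 9.1.2: R/E.
- Rate with the resection condition: (R − j)/(E − k).
- If j = 0, the ratio of the two is E/(E − k).
- In general the resection condition raises the rate when j/k < R/E and lowers it when j/k > R/E.

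The documents give no expected RECIST rate and no expected number unresected, so R, j and k are assumptions. E = 31 further assumes that all 31 planned patients are evaluable under 9.1.2.

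| R (j = 0) | k = 0 | k = 1 | k = 3 | k = 6 |
|---|---|---|---|---|
| 3 | 9.7% | 10.0% | 10.7% | 12.0% |
| 6 | 19.4% | 20.0% | 21.4% | 24.0% |
| 8 | 25.8% | 26.7% | 28.6% | 32.0% |
| Ratio 31/(31 − k) | 1.00 | 1.03 | 1.11 | 1.24 |

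**Reversal.** With R = 6, k = 3 and j = 1, the resected-only rate is (6 − 1)/(31 − 3) = 5/28 = 17.9%, below 6/31 = 19.4%. This agrees with the general condition, since j/k = 33.3% exceeds R/E = 19.4%.

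**The case against.** A reader might infer that any patient whose scan shows progression leaves the denominator, so that the RECIST rate is necessarily inflated. The documents do not support that.

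- Only non-resection removes a patient. Section 3.3 provides for patients with radiographic progression at the postoperative visit, so resected progressors are foreseen, and they remain as non-responders.
- The stopping rule in Section 4.3 ("Radiographic and/or symptomatic deterioration attributed to disease progression disease as determined by the investigator") ends study treatment and does not say that surgery is cancelled. The schedule puts the pre-surgery scan at days 57–64, after the second and last planned durvalumab dose on day 43.
- Section 1.6.2 names toxicity as something that may prevent surgery. That can remove responders as well as non-responders, and the EGFR exclusion can move the rate either way.

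A reader might also infer that the reported progression rate is understated or that the PD-L1 comparison is biased in a known direction. Progression rate is not a planned endpoint, and the PD-L1 comparison is a difference between two groups that can each lose patients, so its direction is undetermined.

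It can further be said that the two sections do different jobs: 9.1.2 says whose scan can be classified, 11.1.2 says who is analysed. That yields the intersection of the two sets, and a scanned but unresected patient still drops out. Finally, RECIST response drives no decision in this trial.

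These points remove the certainty and limit the consequence. They do not remove the conflict between the two definitions or justify conditioning a pre-surgery scan on later surgery.

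**Conclusion.** The point holds as a conflict between two analysis-set definitions, with a conditional bias attached. For the same secondary endpoint, Section 9.1.2 gives a set that does not require surgery and Section 11.1.2 a set that does; the second also removes EGFR-mutant tumors, and no text settles which applies.

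If every unresected patient is a non-responder, the resection condition multiplies the rate by 31/(31 − k): no effect at k = 0, up to 1.24 at k = 6 (for example 19.4% becoming 24.0%). This rests on assumed values of k and on all 31 patients being evaluable under 9.1.2. Upward bias is the more likely direction, because progression may cost a patient surgery while response should not. It is not certain, and a single unresected responder among three can reverse it. The pCR analysis, N = 31 and both stage rules are untouched.

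**What to change.** - In Section 11.1.2 and the synopsis, state that the resection condition does not apply to RECIST response.
- Define one RECIST set: all patients with measurable disease at baseline who received at least one dose of durvalumab, resected or not. Keep the plan's EGFR exclusion for this set unless the sponsor decides otherwise.
- Count progression, death before the scan and absence of a repeat scan as non-response. This also closes the gap for treated patients who are never re-scanned.
- Rewrite the paragraph of Section 9.1.2 on evaluability for objective response to match, and name the same set in Section 11.2.2.
- Report the resected-only rate as a sensitivity analysis.

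The set still starts at the first durvalumab dose, as 11.1.2 does now, so patients who receive only sirolimus remain outside it. The cost is wording in the protocol and synopsis; no additional scans, patients or data are needed. The downside is that the reported response rate may be somewhat less favourable.

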10. ASSESSMENT OF SAFETY

10.1.1 Clinical laboratory tests

Blood and urine samples for determination of clinical chemistry, hematology, and urinalysis will be taken at the times indicated in the assessment schedules and as clinically indicated (see the SoAs). Samples will be run at the clinic/hospital site utilized by each patient. Laboratory values outside reference ranges will be reviewed by a study investigator.

Clinical laboratory safety tests, including serum pregnancy tests, will be performed in a licensed clinical laboratory according to local standard procedures. Sample tubes and sample sizes may vary depending on the laboratory method used and routine practice at the site. Pregnancy tests may be performed at the site using a licensed test (urine or serum pregnancy test). Abnormal clinically significant laboratory results should be repeated as soon as possible (preferably within 24 to 48 hours).

Additional safety samples may be collected if clinically indicated at the discretion of the Investigator. The date, time of collection, and results (values, units, and reference ranges) will be recorded on the appropriate eCRF.

The laboratory variables to be measured are presented in Table 7 (hematology), Table 8 (chemistry), and Table 9 (urinalysis).

Other safety tests to be performed at screening include assessment for hepatitis B surface antigen, hepatitis C antibodies, and HIV antibodies.

The following laboratory variables will be measured:

Table 7. Hematology Laboratory Tests

Basophils	Mean corpuscular volume
Eosinophils	Monocytes
Hematocrit	Neutrophils
Hemoglobin	Platelet count
Lymphocytes	Red blood cell count
Mean corpuscular hemoglobin	Total white cell count
Mean corpuscular hemoglobin concentration	

Note: For coagulation parameters, activated partial thromboplastin time and international normalized ratio are to be assessed at baseline on Day 0 (unless all screening laboratory haematology assessments are performed within 3 days prior to Day 0), and as clinically indicated.

Clinical Study Protocol

Investigational Drug Substance: MEDI4736 Sirolimus (Rapamune)

Study Number **19-20015**

Edition Number: 4

Date: **11 February 2022**

^a Can be recorded as absolute counts or as percentages. Absolute counts will be calculated by DM if entered as percentage. Total white cell count therefore has to be provided.

Table 8. Clinical Chemistry (Serum or Plasma) Laboratory Tests

Albumin	Glucose
Alkaline phosphatase	Lactate dehydrogenase
Alanine aminotransferase	Lipase
Amylase	Magnesium
Aspartate aminotransferase	Potassium
Bicarbonate	Sodium
Calcium	Total bilirubin ^a
Chloride	Total protein
Creatinine	Urea or blood urea nitrogen, depending on local practice
Gamma glutamyltransferase	Uric acid

Tests for ALT, AST, alkaline phosphatase, and total bilirubin must be conducted and assessed concurrently. If total bilirubin is $\geq 2 \times$ upper limit of normal (and no evidence of Gilbert's syndrome) then fractionate into direct and indirect bilirubin.

^b It is preferable that both amylase and lipase parameters are assessed. For sites where only 1 of these parameters is routinely measured then either lipase or amylase is acceptable.

^c gamma glutamyltransferase, and magnesium testing are to be performed at baseline, on Day 0 (unless all screening laboratory clinical chemistry assessments are performed within 3 days prior to Day 0), and if clinically indicated.

^d Creatinine Clearance will be calculated by data management using Cockcroft-Gault (using actual body weight).

^e If TSH is measured within 14 days prior to Day 1 (first infusion day), it does not need to be repeated at day Free T3 or free T4 will only be measured if TSH is abnormal or if there is a clinical suspicion of an AE related to the endocrine system

Table 9. Urinalysis Tests^a

Bilirubin	pH
Blood	Protein
Glucose	Specific gravity
Ketones	Colour and appearance

^a Microscopy should be used as appropriate to investigate white blood cells and use the high-power field for red blood cells

Clinical Study Protocol

Investigational Drug Substance: MEDI4736 Sirolimus (Rapamune)

Study Number **19-20015**

Edition Number: 4

Date: **11 February 2022**

If a patient shows an AST or ALT $\geq 3 \times \text{ULN}$ together with total bilirubin $\geq 2 \times \text{ULN}$, refer to **Error!**

Reference source not found. for further instructions on cases of increases in liver biochemistry and evaluation of Hy's Law. These cases should be reported as SAEs if, after evaluation, they meet the criteria for a Hy's law case or if any of the individual liver test parameters fulfill any of the SAE criteria.

All patients should have further chemistry profiles performed at the post-surgery, end of treatment visit.

Any clinically significant abnormal laboratory values should be repeated as clinically indicated and recorded on the eCRF. Situations in which laboratory safety results should be reported as AEs are described in Section 10.5.

All patients with Grade 3 or 4 laboratory values at the time of completion or discontinuation from IP must have further tests performed until the laboratory values have returned to Grade 1 or 2, unless these values are not likely to improve because of the underlying disease.

10.1.2 Physical examinations

Physical examinations will be performed according to the assessment schedules (see the SoAs). Full physical examinations will include assessments of the head, eyes, ears, nose, and throat and the respiratory, cardiovascular, GI, musculoskeletal, neurological, dermatological, hematologic/lymphatic, and endocrine systems. Height will be measured at screening only. Targeted physical examinations are to be utilized by the Investigator on the basis of clinical observations and symptomatology. Situations in which physical examination results should be reported as AEs are described in Section 10.5.

Resting 12-lead ECGs will be recorded at screening and as clinically indicated throughout the study. ECGs should be obtained after the patient has been in a supine position for 5 minutes and recorded while the patient remains in that position.

In case of clinically significant ECG abnormalities, including a QTcF value >470 ms, 2 additional 12-lead ECGs should be obtained over a brief period (eg, 30 minutes) to confirm the finding.

Situations in which ECG results should be reported as AEs are described in Section 10.5

At Screening, a single ECG will be obtained on which QTcF must be <470 ms.

In case of clinically significant ECG abnormalities, including a QTcF value >470 ms, 2 additional 12-lead ECGs should be obtained over a brief period (e.g., 30 minutes) to confirm the finding.

Situations in which ECG results should be reported as AEs are described in Section 10.

Clinical Study Protocol

Investigational Drug Substance: MEDI4736 Sirolimus (Rapamune)

Study Number **19-20015**

Edition Number: 4

Date: **11 February 2022**

10.1.3 Vital signs

Vital signs (blood pressure [BP], pulse, temperature, and respiration rate) will be evaluated according to the SoAs. Body weight is also recorded at each visit along with vital signs.

First infusion

On the first infusion day, patients will be monitored and vital signs collected/recorded in eCRF prior to, during and after infusion of IP as presented in the bulleted list below.

BP and pulse will be collected from patients in the I-O arms before, during, and after each infusion at the following times (based on a 60-minute infusion):

Prior to the beginning of the infusion (measured once from approximately 30 minutes before up to 0 minutes [i.e., the beginning of the infusion])

Approximately 30 minutes during the infusion (**halfway** through infusion)

At the end of the infusion (approximately 60 minutes \pm 5 minutes)

If the infusion takes longer than 60 minutes, then BP and pulse measurements should follow the principles as described above or be taken more frequently if clinically indicated. A 1-hour observation period is recommended after the first infusion of durvalumab.

Subsequent infusions

BP, pulse and other vital signs should be measured, collected/recorded in eCRF prior to the start of the infusion. Patients should be carefully monitored and BP and other vital signs should be measured during and post infusion as per institution standard and as clinically indicated.

10.1.4 Early patient review for safety

Patients will be seen in close interval follow-up (Cycle 1 Day 8, Cycle 2 Day 8, and during surgical window to ensure early identification and management of toxicities.

10.1.5 WHO/ECOG performance status

ECOG performance status will be assessed at the times specified in the assessment schedules (see the SoAs) based on the following:

0. Fully active; able to carry out all usual activities without restrictions
1. Restricted in strenuous activity, but ambulatory and able to carry out light work or work of a sedentary nature (e.g., light housework or office work)

Clinical Study Protocol

Investigational Drug Substance: MEDI4736 Sirolimus (Rapamune)

Study Number **19-20015**

Edition Number: 4

Date: **11 February 2022**

2. Ambulatory and capable of self-care, but unable to carry out any work activities; up and about more than 50% of waking hours.
3. Capable of only limited self-care; confined to bed or chair more than 50% of waking hours
4. Completely disabled; unable to carry out any self-care and totally confined to bed or chair
5. Dead

Any significant change from baseline or screening must be reported as an AE.

